### APPENDIX 3. DRAIZE SCALE

- *Study Personnel Instructions:* The modified Draize Scale as shown in the table below will be used for physical examination/rating of abnormalities at the injection site.
- The injection site should be examined for formation of both erythema and edema and results recorded in the Case Report Form. Evaluations of the injection site should be performed at  $10 \pm 5$  and  $30 \pm 5$  minutes post-treatment, and again at the end of the treatment visit (i.e., at  $240 \pm 5$  minutes post-dosing) if any scores  $> 0$  were noted at 30-minutes post-dosing.

Erythema Formation		Edema Formation	
Description	Score	Description	Score
No erythema	0	No edema	0
Very slight erythema Barely perceptible	1	Very slight edema Barely perceptible	1
Well defined erythema	2	Well defined edema	2
Moderate erythema	3	Moderate edema Raised approx. 1 mm	3
Severe erythema Beet redness to slight eschar formation	4	Severe edema Raised more than 1 mm and beyond exposure area	4

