  - d. Every 5±2 minutes after glucagon is administered until all symptoms have abated (i.e., all symptoms have score = 1) or 45 minutes post-dosing, whichever occurs first.
9. Local tolerability will be assessed as follows:
  - a. Subjects will complete a Visual Analog (VAS) questionnaire regarding injection site discomfort ([Appendix 2](#)) at 10±5 and 30±5 minutes post-dosing, and again at 240±5 minutes post-dosing if VAS score reported at 30 minutes is > 0 mm.
  - b. Subjects will complete an Injection Site Discomfort Description and Duration Questionnaire at 10±5 minutes post-dosing. If discomfort is ongoing at 10 minutes post-dosing, the questionnaire will be updated before the subject leaves the clinic to document the final duration.
  - c. An investigator will use the modified Draize scales ([Appendix 3](#)) to assess erythema and edema formation at the injection site at 10±5 and 30±5 minutes following administration. Any injection site with a score > 0 for either erythema or edema at 30 minutes post-dosing will be re-evaluated for both at 240±5 minutes post-dosing. If any scores remain > 1 at the 240-minute evaluation, the subject may leave the clinic but will be instructed to contact study staff if the condition fails to resolve.
10. Adverse events reported by the subject or observed by an investigator will be recorded in the CRF.

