### 12.2. Reporting Adverse Events

All observed or volunteered AEs regardless of treatment group or suspected causal relationship to the study treatment will be reported with two exceptions. Since it is being experimentally induced in this study, hypoglycemia will not be considered an AE in this study unless the event meets one of the definitions of an SAE (see Section 12.4). Injection site reactions will not be considered an AE unless a skin reaction or pain requires medical intervention.

For all AEs, the investigator must pursue and attempt to obtain information adequate to determine the outcome of the AE and to assess whether it meets the FDA criteria for classification as an SAE, requiring immediate notification to Xeris Pharmaceuticals. For all

AEs, follow-up by the investigator is required until the event resolves or stabilizes at a level acceptable to the investigator to consider it closed. For an unresolved AEs to be considered stable, the Medical Monitor must concur with that assessment.

As part of ongoing safety reviews conducted by the Sponsor, any non-serious adverse event that is determined to be serious (according to the FDA definitions of an SAE) will be reported by the Sponsor as an SAE. To assist in the determination of case seriousness, further information may be requested from the investigator to provide clarity and understanding of the event in the context of the clinical study.

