### **13.3. Safety Analysis**

All safety analyses will be performed using the safety cohort of subjects, namely those subjects receiving at least one dose of the study medication.

The following variables will be compared between the treatments for safety purposes:

- Adverse events and serious adverse events
- Laboratory safety variables (Screening to Final Visit)
- Physical examination (Screening to Final Visit)
- Vital signs
- Body weight (Screening to Final Visit)

- ECG (Screening to Final Visit)
- Local tolerability, including:
  - Subjective injection site discomfort as reported by subjects using a 100-mm VAS and ordinal pain scales ([Appendix 2](#)).
  - Erythema and or edema formation at site of injection assessed using the Draize scale ([Appendix 3](#))

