#### **13.3.6. Local Tolerability:**

The incidence of any injection site discomfort (score >0 on the ordinal rating scale) will be analyzed descriptively. The incidences of erythema and edema will be analyzed in a similar manner. Descriptive statistics (only) will be provided for time of onset and duration (of discomfort) and discomfort description (i.e., pain, irritation, itching, etc.). Mean VAS scores will be compared between the treatments.

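### Draize erythema and edema are graded 0–4, but Section 13.3.6 specifies only their incidence, so the protocol names no summary of skin-reaction grade by product

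*Combined protocol and SAP*

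**What the plan says.** **Collection.** Appendix 3 scores erythema and edema separately from 0 to 4. Grade 1 is a very slight change and grade 4 for erythema is "Severe erythema Beet redness to slight eschar formation". Section 10.2.1, item 9(c), schedules the assessment at 10 and 30 minutes after each dose. "Any injection site with a score > 0 for either erythema or edema at 30 minutes post-dosing" is examined again at 240 minutes. The same item gives a separate instruction for subjects whose score is still above 1 at 240 minutes.

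**Analysis.** Section 13.3 introduces its list with "The following variables will be compared between the treatments for safety purposes", and the list includes "Erythema and or edema formation at site of injection assessed using the Draize scale". It names no measure. Section 13.3.6 supplies one. It first says "The incidence of any injection site discomfort (score >0 on the ordinal rating scale) will be analyzed descriptively", then "The incidences of erythema and edema will be analyzed in a similar manner". For intensity it adds only "Mean VAS scores will be compared between the treatments".

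**Adverse events.** Section 12.2 states: "Injection site reactions will not be considered an AE unless a skin reaction or pain requires medical intervention". Section 12.5 has adverse events graded mild, moderate or severe on the CRF. Section 13.3.1 summarizes them by system organ class and study drug and mentions no breakdown by severity.

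**Deferred detail.** The end of Section 13.5 leaves finer detail of the analyses in Sections 13.1 to 13.5 to an SAP. The combined document contains no separate SAP text.

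**The concern.** Comparing safety and tolerability is a secondary objective (Section 5.2), and Draize erythema and edema are listed safety endpoints (Section 5.3.2). The two injections differ locally: 0.2 mL of a non-aqueous DMSO solution from an auto-injector against 1 mL reconstituted with sterile diluent (Sections 9.3.1 and 9.3.3). How marked the skin reactions are is therefore a natural question for this comparison, and the grades needed to answer it are recorded.

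Incidence alone does not answer it. If both products often leave a faint mark, the incidence table can agree closely while one product produces more well-defined or severe reactions. Discomfort receives both an incidence and an intensity comparison; the visible reaction receives incidence only.

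**Working it through.** The documents give no figure for erythema or edema rates, so there is none to reproduce. The check has two parts.

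**1. Does any named output carry the Draize grade by product?**

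| Output | Source | Carries the grade? |
|---|---|---|
| Incidence of erythema, edema | 13.3.6 | No, if incidence means score above 0 |
| Comparison of Draize findings | 13.3 | Measure not stated |
| Mean VAS | 13.3.6, Appendix 2 | No; subject-reported discomfort |
| Adverse event table | 12.2, 13.3.1 | Only reactions needing intervention; no severity table named |
| End-of-text listings | 13.3.2, 13.3.5 | Laboratory and ECG only |
| Follow-up visit | 10.2.3 | No Draize assessment named |

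No row names a summary by grade. Section 10.2.1, item 9(c), does separate scores above 1 from lower scores at 240 minutes, so a cut at grade ≥2 has a precedent in the protocol.

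**2. What can incidence hide?** These rates are assumed, purely to show the mechanism: grade ≥2 in 40% on product A and 15% on product B; any erythema in 80% on both; n = 75 pairs. The figure 75 is the completer target. The synopsis requires evaluable results for only one period, so the number of pairs could be lower.

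- Difference in any-grade incidence: 0.80 − 0.80 = 0.
- Difference in grade ≥2: 0.40 − 0.15 = 0.25.

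The variance of a paired difference d depends on the discordant proportions b (A only) and c (B only): SE = √[(b + c − d²)/n]. With d fixed at 0.25:

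| Within-subject association | b | c | SE | 1.96 × SE |
|---|---|---|---|---|
| Maximal overlap | 0.25 | 0 | √(0.1875/75) = 0.050 | 0.098 |
| Independent | 0.34 | 0.09 | √(0.3675/75) = 0.070 | 0.137 |
| No overlap | 0.40 | 0.15 | √(0.4875/75) = 0.081 | 0.158 |

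The independent row agrees with √[(0.40 × 0.60 + 0.15 × 0.85)/75] = 0.070. In all three rows the interval for grade ≥2 excludes 0, while the incidence difference is 0.

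**Range over the assumed incidence.** With grade ≥2 at 40% and 15%, any-grade incidence can be anywhere from 40% to 100% on A and from 15% to 100% on B. The incidence difference can therefore run from 40 − 100 = −60 points to 100 − 15 = +85 points. Equal incidence is possible at any common value from 40% to 100%, so masking does not require a ceiling. Equally, the incidence table might show a difference. Incidence simply does not determine the grade comparison.

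**The case against.** The strongest reply is that the documents do not rule out a grade summary. Section 13.3 promises a comparison of Draize findings without restricting it to yes/no, and Section 13.5 defers detail to an SAP; table layout is the kind of thing an SAP settles. This stands as a limit on the claim. A reader might infer that no analysis of severity is planned at all. The documents support only the narrower statement that the protocol text names none. The one measure that text does specify is incidence, so a grade summary would rest on a later choice.

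Second, the phrase in Section 13.3.6 linking erythema and edema to the discomfort analysis may mean only that they too are described without testing. No Draize cut-off is written down. That is fair: score above 0 is the most natural reading, not the only one. It also means that incidence is undefined for these endpoints, which itself needs correcting.

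Third, a reader might take Section 12.2 to remove all injection-site reactions from the adverse event tables. It does not. Reactions needing medical intervention are adverse events and are tabulated by study drug. What is lost is the grade of reactions that need no intervention and, since no severity table is named, any severity display for those that do.

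Fourth, the illustrative rates have no basis in the documents, and incidence was set equal by construction. This also stands. Section 13.3.6 further plans to describe the type, onset and duration of discomfort, so tolerability does not rest on erythema incidence alone. It would be wrong to infer that the trial will report the products as locally similar when they are not.

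The objection that a grade ≥2 cut is arbitrary does not stand, given the instruction for 240-minute scores above 1.

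**Conclusion.** The point holds for the protocol text. Section 13.3.6 specifies descriptive incidence for two endpoints collected on a five-level scale, and neither the adverse event tables nor the mean VAS recovers the grade of the skin reaction. The conclusion rests on reading incidence as score above 0, and on no SAP text adding a grade summary.

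The 80%/80% and 40%/15% rates illustrate how a 25-point difference could go unseen; they are not an expected result and say nothing about which product, if either, is worse. The matter concerns a secondary descriptive safety output. The primary analysis, sample size and conduct are unaffected, and no data are lost because the grades are in the CRF. The change is worth making because it serves a stated objective at almost no cost.

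**What to change.** In Section 13.3.6 (or the SAP, before unblinding):

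- State that incidence of erythema or edema means a Draize score ≥1 at any post-dose assessment.
- For erythema and edema separately, tabulate each subject's worst post-dose grade (0–4) by treatment, with cumulative counts for ≥1, ≥2, ≥3 and 4. Say that the worst grade is taken over 10 and 30 minutes, plus 240 minutes where that assessment was triggered.
- For subjects who received both products, cross-tabulate G-Pen grade against Lilly grade. Give the paired difference in the proportion with grade ≥2 and a 95% CI computed from the discordant pairs, using a score-type interval if those pairs are few. Label it descriptive, with no hypothesis test.
- List every grade 3–4 score by treatment and time point.

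The cost is two tables, each with an erythema and an edema panel, and one listing, all from data already collected. Visits, procedures and sample size do not change.

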## **APPENDIX 4. INSTRUCTIONS FOR USE**
